**Principle Investigator: [name]**

**Co-Investigators: [name]**

**[name]**

**REB17-2317**

**December 5, 2017**

## Peripherally inserted central venous catheter insertion site and complication rates in neonates: a randomized controlled trial

### 1. Background and rationale

#### 1.1. PICC lines as ‘life lines’ in neonates

Peripherally inserted central venous catheters (PICCs) provide lasting venous access to deliver total parenteral nutrition (TPN) and medications for neonates receiving intensive care, especially in very low-birth-weight infants. In neonates, PICC lines are commonly inserted at the basilic, cephalic, and axillary veins in the upper extremity, the great saphenous and popliteal veins in the lower extremity, and the temporal and posterior auricular veins in the scalp. The incidence of PICC associated complication rates in literature varies from 27 to 42%. The common complications resulting in removal of PICCs include mechanical complications such as line infiltration, line occlusion, thrombosis, central line-associated bloodstream infection (CLABSI), and life-threatening complications such as pericardial effusion and tamponade and pleural effusion.

#### 1.2. PICC related complication reports with site of insertion

Usually the site of insertion is chosen based on the inserter’s preference and accessibility of veins rather than incidence of complications. In adult literature, it has been reported that lower extremity PICCs are associated with a higher risk of infection than upper extremity PICCs, and it is recommended to avoid femoral sites in adults. However, studies in pediatric patients have demonstrated that femoral catheters have a low incidence of mechanical complications and might have an equivalent infection rate to that of non-femoral catheters. In neonates, only a few retrospective studies have reported complication rates based on the site of insertion with conflicting results. In a retrospective study, Hoang et al reported that upper extremity PICCs had significantly higher rates of *coagulase negative staphylococcal* septicemia and cholestasis as compared to lower extremity PICCs in neonates. Wrightson reported no difference in the overall complication rate between upper and lower extremity PICCs (27% vs 21%). Presumed sepsis was the most common complication requiring PICC removal. Both studies included infants of all gestational ages (including term infants) and all the PICCs inserted. It is possible that a higher number of PICCs inserted in a single baby may increase the complication rates. Ozkiraz et al also reported no difference in complications between upper and lower extremity PICCs in very low-birth-weight and extremely low-birth-weight infants. Some studies in preterm infants recommended avoiding PICCs in the lower limbs, especially at the femoral site because of a high incidence of sepsis and thrombosis. Our retrospective study in Calgary noted that the overall rate of catheter-related complications resulting in PICC removal was not significantly different between upper and lower extremity PICCs. However, there was a 2.4-fold increase in odds of line infiltration among upper extremity PICCs, especially on the right side. Line occlusion was more common in lower extremity PICCs.

#### 1.3. Non-central catheter tip position associated with complications

When the tip of PICC is not at the superior or inferior vena cava, it is called non central catheter tip position. The mid-clavicular tip position of central lines is more commonly associated with line infiltrations. In a study by Jain et al, non-central PICCs developed more complications in less time, leading to non-elective catheter removal. Similarly, Racadio et al

reported a sevenfold increased risk of complications when the catheter tip was non-central in pediatric populations. Use of high-osmolar TPN solutions infusing through PICC lines might have contributed to the infiltrations, especially if the catheter tips were non-central (midclavicular location). The details of these potential factors are not available from retrospective studies. Likewise, catheter tip position has not always been documented in retrospective studies.

#### **1.4. Thrombosis as a complication of PICC lines**

In adults, it is reported that spontaneous deep venous thrombosis occurs more commonly on the left side as compared to the right side. However, in neonates, there is no uniform policy to assess thrombosis. It has been observed that lower extremity PICCs had a higher rate of major venous thrombo-embolism especially in neonates with intra-abdominal surgeries. Likewise, infiltration and phlebitis were commonly seen with lower limb PICCs in neonates with gastroschisis during silo reduction and within 5 days of abdominal closure.

#### **1.5. Relation of catheter insertion site to tip position**

Proximity of insertion site to catheter tip destination has been suggested to be a factor against PICC-related complications. Panagiotounakou et al observed that PICCs inserted through axillary veins were associated with 12 times less complications and were 7 times electively removed due to achievement of full enteral nutrition as compared with the PICCs inserted through forearm veins due to proximity of insertion site to catheter tip destination. Tsai et al reported that culture-proven sepsis was common with femoral PICCs, whereas non-infectious complications were common with non-femoral PICCs.

#### **Rationale for the study:**

There are no prospective or randomized clinical studies in the literature that have looked at the site of PICC insertion and complication rates in neonates. Earlier retrospective studies also included all PICC lines irrespective of the timing of insertion or number of catheters used on an individual patient. Retrospective studies lack pertinent information to determine why the site was chosen and details of complication types. A well-designed prospective randomized clinical trial is required to conclusively establish if PICC site placement is a factor affecting complications that necessitate non-elective removal of the device. Moreover this study will also help in understanding the specific complication such as thrombosis related to PICC line.

## **2. Research Question**

In neonates who require PICC placement as a part of their care in NICU, does complications following PICC insertion resulting in early (non-elective) removal of catheter differ based on the site of insertion?

P: Neonates admitted to the NICU

I: Lower extremity PICCs

C: Upper extremity PICCs

O: Any complication necessitating non-elective removal of lines

T: During the period of PICC insertion

### 3. Study hypothesis:

We hypothesize that there is an association between the site of PICC insertion and the complications necessitating PICC line removal non-electively and complications rates are different between upper extremity and lower extremity PICCs.

### 4. Study objective:

- i) To examine whether the complications following PICC insertion resulting in early removal differ based on the site of insertion

### 5. Methods:

**5.1. Study design:** Parallel group, prospective, randomized controlled trial

**5.2. Description of population:** All neonates admitted to the level III neonatal intensive care unit (NICU), Calgary, Canada (i.e. Foothills Medical Centre (FMC) and Alberta Children's Hospital (ACH), will be eligible for the study and will be screened for participation. Randomization will be done once inclusion criteria are met, in the absence of exclusion criteria and once informed consent is obtained.

#### 5.3. Inclusion criteria:

- Neonates of all gestational ages admitted to Foothills Medical Centre and Alberta Children's Hospital NICU
- PICC line insertion planned as part of NICU care
- Venous access available in both upper (above umbilicus) and lower body

#### 5.4. Exclusion criteria:

- Local infection at potential site of insertion
- Hemangioma, lymphangioma or malformations in the region of insertion
- Major chromosomal anomalies

#### 5.5. Randomization:

Eligible infants will be randomly assigned for upper extremity or lower extremity PICC insertion using an allocation ratio of 1:1. We will use blocked randomization of varying block sizes in multiples of two. The investigators will be blinded to the block sizes; but the block sizes will ensure appropriate balance between both arms. Infants will be stratified into two groups based on the gestational age ( $\leq 32$  weeks,  $>32$  weeks). Randomization will be performed using computer generated software once eligibility is confirmed and informed consent is obtained. A unique patient identification number and the randomisation sequence will be generated.

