## 7. Statistical analysis:

### 7.1. Sample size calculation:

Based on our previous retrospective study, the rate of PICC complication resulting in removal of PICC was 30%. In order to find a clinically important difference of 10% between PICCs inserted through upper extremity and lower extremity, a sample of 153 infants in each group will be required at 80% power and alpha error of 5%. We will recruit 320 infants. . Approximately 200-250 PICCs are inserted per year in Calgary NICUs. We expect to complete recruitment over 18 month's period.

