## 7.2. Statistical methods:

Data will be analyzed using intention-to-treat analysis. Baseline demographics of the study population will be described using descriptive statistics. Data will be checked for normality. Categorical variables will be presented as counts and percentages and continuous variables as mean and standard deviation or median and inter-quartile range if data are not normally distributed. Primary outcome, which is the presence of any complication, necessitating PICC removal, is a binary outcome where we will use chi-squared test or Fisher exact test. Event rates, relative risk and 95% confidence intervals will be reported for primary outcome. Secondary outcome, which is the time from PICC insertion to development of complication, is a continuous outcome for which two sided independent samples t-test or Mann-Whitney U test, depending on if the data is normally distributed or not. Standard deviation and 95% confidence interval will be reported for continuous outcomes. We will also calculate time to complication post insertion as median time. We will also do multivariate logistic regression analysis to examine the association of PICC site and complication rate after adjusting for gestational age, day of PICC insertion and illness severity score. P-value <0.05 will be taken as significant. Stata 15 will be used for the analysis.

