## 8. Trial administration:

**8.1. Clinical Site:** This multicentre study will be conducted at the Neonatal Intensive Care Unit, in Foothills Medical Center and Alberta Children's Hospital NICU, Calgary, Canada

**8.2. Steering Committee and Local Operations Group:** The steering committee will consist of two neonatologists, two transport nurses, one Clinical Trials Coordinator and one nurse clinician. Along with these, there will be a study physician committed to the trial and a research assistant responsible for the daily conduct of the trial including recruitment, informed consent, administration of intervention, data collection, and in-servicing of relevant NICU staff.

**8.3. Data Safety Monitoring Board (DSMB):** This committee will be made up of two separate neonatologists, a statistician, and a unit manager, who will be blinded to the two groups. They will function independently from the study investigators. Once half the intended recruitment is reached, an interim analysis of clinical outcome data for efficacy and data analysis for expected and unexpected adverse events will be done. The DSMB will recommend termination of the trial for statistically significant ( $p < 0.001$ ) differences between the intervention groups with respect to PICC related complications, mortality, or serious unexpected adverse events. Results of the interim analysis will not be disclosed to investigators or study participants but will be published along with the DSMB's recommendations upon completion of the trial.

**8.4. Data Collection:** All data collection will be done with the help of a research assistant, supervised by a physician who is committed to the study. The study physician will check the data collection forms for completeness of data and fill each form separately. The study data will be collated and entered into the study database for analysis. Completed data collection forms and all the reporting forms will be securely locked in a closed cabinet in the study Principal Investigator's office at FMC.

**8.5. Study Monitoring:** The specific committee will ensure that all study procedures are in compliance with good clinical practice. It is imperative that the study proposal and all the amendments will be approved by the local Research Ethics Board.

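### Hospital is left out of the randomisation strata and of every analysis in this two-hospital trial, and the primary test ignores the stratified design: no bias results, but a small, nearly free gain in precision is passed up

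*Combined protocol and SAP*

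**What the plan says.** - **Sites.** Section 8.1: "This multicentre study will be conducted at the Neonatal Intensive Care Unit, in Foothills Medical Center and Alberta Children's Hospital NICU". Sections 5.2 and 5.3 name the same two hospitals.
- **Randomisation.** Section 5.5 allocates "using an allocation ratio of 1:1" and adds: "We will use blocked randomization of varying block sizes in multiples of two". On strata it says: "Infants will be stratified into two groups based on the gestational age". The cut is at 32 weeks, and hospital is not mentioned.
- **Primary analysis.** Section 7.2 says that the primary outcome "is a binary outcome where we will use chi-squared test or Fisher exact test". A relative risk with a 95% confidence interval is to be reported. No stratification or adjustment is attached to either.
- **Adjusted analysis.** Section 7.2 adds a logistic regression for insertion site "after adjusting for gestational age, day of PICC insertion and illness severity score". Hospital is not in that list.

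The protocol gives no reason for leaving hospital out, and it does not plan a subgroup analysis by hospital.

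**The concern.** Each infant's hospital is known before randomisation, and admission to one of the two units is itself an inclusion criterion. Blocking within gestational-age groups does not guarantee that the arms are balanced within each hospital. If complication rates differ between the hospitals, any chance imbalance moves the estimated difference between upper- and lower-limb lines a little. Because no analysis includes hospital, nothing removes that variation afterwards.

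The primary test has a related gap. The design balances the arms on gestational age, but the test and relative risk that carry the main conclusion are computed as if there were no strata. The logistic model includes gestational age, but it is an additional analysis and does not alter the primary result.

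What is at stake is modest: some precision, and having the adjustment fixed in advance rather than chosen later if the arms turn out uneven by hospital.

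**Working it through.** The plan states no figure for the effect of hospital, so there is none to reproduce.

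**Inputs from the protocol.** Recruitment of 320 infants, allocated 1:1, so 160 per arm; a reference complication rate of 30%; a target difference of 10 points (section 7.1), taken here as 30% against 20%; significance level 0.05 (section 7.2).

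**Assumptions, because the documents do not give them.** The larger hospital's share of infants (50% to 85%) and the gap between hospital complication rates (0 to 20 points).

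**Step 1: chance imbalance by hospital.** With share *s* at one hospital, the SD of the between-arm difference in that share is √[s(1 − s)(1/160 + 1/160)]. For s = 0.30 this is √(0.21 × 0.0125) = 0.051, or 5.1 points.

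**Step 2: effect on the risk difference.** Multiply that SD by the gap in hospital rates.

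| Split between hospitals | SD of imbalance | Added SD, 10-point gap | Added SD, 20-point gap |
|---|---|---|---|
| 50/50 | 5.6 points | 0.56 point | 1.12 points |
| 70/30 | 5.1 points | 0.51 point | 1.02 points |
| 85/15 | 4.0 points | 0.40 point | 0.80 point |

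**Step 3: compare with the total sampling error.** At 30% against 20%, the standard error of the risk difference is √(0.30 × 0.70/160 + 0.20 × 0.80/160) = √(0.37/160) = 0.048, or 4.8 points. For the 70/30 split:

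- 20-point gap: (1.02/4.81)² = 0.045, so 4% to 5% of the variance. Removing it would shrink the standard error by 1 − √(1 − 0.045), about 2%.
- 10-point gap: (0.51/4.81)² = 0.011, about 1% of the variance.

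**Step 4: simulation.** 40,000 trials per scenario, 160 per arm, overall rate 30% before any treatment effect, allocation not stratified by hospital. The crude chi-squared test is compared with a Mantel-Haenszel test stratified by hospital. Power is for a 10-point reduction in one arm.

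| Larger hospital | Gap (points) | Type I error, crude / stratified (%) | Power, crude / stratified (%) |
|---|---|---|---|
| 50% | 0 | 4.96 / 4.92 | 54.93 / 54.52 |
| 50% | 10 | 5.04 / 5.02 | 54.55 / 54.57 |
| 50% | 20 | 5.17 / 5.05 | 54.74 / 56.45 |
| 70% | 0 | 5.00 / 4.96 | 54.40 / 53.96 |
| 70% | 10 | 5.05 / 5.02 | 54.74 / 54.74 |
| 70% | 20 | 4.98 / 4.88 | 55.01 / 56.54 |
| 85% | 0 | 4.95 / 4.93 | 54.82 / 54.42 |
| 85% | 10 | 5.01 / 5.00 | 54.82 / 54.69 |
| 85% | 20 | 5.08 / 4.96 | 54.88 / 55.60 |

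Type I error is about 5% either way. The change in power is about zero at gaps of 0 to 10 points (at worst 0.4 point lower) and 0.7 to 1.7 points higher at a gap of 20. The simulation covers the change in analysis only. It does not model stratified allocation or the gestational-age strata, for which the protocol gives no separate rates.

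The power level near 55% differs from the 80% in section 7.1. That is a separate sample-size question, which including hospital neither causes nor repairs.

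**The case against.** The strongest case for leaving the plan alone is that nothing is wrong with the inference. Chance imbalance by hospital is ordinary random error, already covered by the unadjusted standard error and confidence interval. This stands, and the simulated error rates confirm it.

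The protocol also points towards shared practice. Section 5.6 refers to certified inserters, standard guidelines and unit policy without distinguishing the hospitals, section 7.1 pools the Calgary units, and section 8.2 sets up one steering committee. A 20-point gap with a 70/30 split and 30% overall would mean hospital rates of about 44% and 24%, or 16% and 36%. Nothing in the documents suggests this, so the larger figures above are an upper illustration.

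More strata also carry a cost. Section 8.8 accepts that the intervention cannot be blinded, and smaller blocked strata leave more incomplete blocks and can make local allocation somewhat easier to guess. With four strata and varying block sizes, this cost is small.

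A reader might infer more than the documents support:

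- **That the result is biased or the p-value invalid.** Randomisation protects both.
- **That this omission explains a lack of power.** The gain is at most about 2 points over the assumed range.
- **That infants with abdominal surgery or gastroschisis (section 1.4) make hospital important.** The documents do not say where these infants are treated. A higher lower-limb risk in them would be effect modification, which a main effect for hospital does not address.
- **That the shift is a sizeable share of the 10-point target.** The relevant comparison is with the 4.8-point standard error.

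What survives is a small inefficiency that costs almost nothing to remove.

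**Conclusion.** The point holds as a minor improvement. Hospital is absent from the strata, the primary test and the logistic model, and the primary test also ignores the gestational-age stratum used in the design. The planned comparison remains unbiased with the correct type I error.

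Under an assumed 70/30 split and a 10- to 20-point gap in hospital rates, the avoidable part is an SD of about 0.5 to 1.0 point within a standard error of about 4.8 points. The corresponding gain in power is about 0 to 2 points. If the hospitals have similar rates, including hospital gains essentially nothing. The split and the gap are both assumptions. That hospital and stratum are missing from the primary analysis can be read directly from sections 5.5 and 7.2.

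**What to change.** 1. **Section 5.5:** stratify by hospital as well as gestational-age group. This gives 2 × 2 = 4 strata, or 320/4 = 80 infants each on average (fewer in some if one hospital recruits much less). Keep the varying block sizes and their concealment from investigators.
2. **Section 7.2, primary analysis:** stratify the test and the relative risk by hospital and gestational-age group, for example with a Mantel-Haenszel test and pooled relative risk with its 95% confidence interval. Changing only the logistic model would leave the primary comparison as it is.
3. **Section 7.2, logistic model:** add hospital to the covariates.
4. **If randomisation has started,** leave the allocation scheme alone and make changes 2 and 3 only, dated before the outcome data are examined by arm.

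The cost is one setting in the randomisation software, one variable known at enrolment and slightly more incomplete blocks. The sample size need not change on this account.

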#### 5.6. Interventions:

PICC insertion attempts will be made by certified health care providers including transport nurses, nurse practitioners and physicians using standard clinical practice guidelines. A maximum of two attempts will be allowed in the designated region, following which further attempts will be considered in the non-designated region if the inserter is confident of success. Number of attempts at insertion and sites of attempts will be recorded as per unit protocol. After the catheter is inserted, catheter tip position will be confirmed by radiograph with the limbs in standard position as per unit protocol, and repeat radiographs will be taken if there is a manipulation. As per unit protocol, the catheter inserter will record the details of the procedure, the type of catheter used, and position of catheter following radiographic confirmation in the progress note of each infant's medical chart. Similarly, the bedside nurse also documents this information in the nursing chart/Metavision. In addition, the inserter will fill out a one-page PICC line tracking sheet for all the lines which includes details such as the indication, date of insertion, site of insertion, catheter tip position, and any complications during insertion. Once the

PICC is removed, the bedside nurse will complete the PICC tracking sheet, filling in the date and the reason for removal of the line.

The clinical goal is to place the catheter tip in the superior vena cava or inferior vena cava, but outside the right atrium. A catheter tip lying beyond the medial end of the clavicle and up to 1 cm at the junction of right atrium and superior vena cava is considered optimal for upper extremity. PICCs with the catheter tip located in the inferior vena cava below the diaphragm are considered optimal for lower extremity PICCs. Heparin will be infused in all PICCs as per standard unit policy. All catheters will be removed either after completion of intravenous therapy or earlier if they develop complications. In all babies an ultrasound will be performed within 72 hours of PICC line removal by neonatologists trained to perform point of care ultrasound, looking for the presence of an occlusive thrombus. If one is detected, consultation to radiology and hematology will be requested as per unit protocol.

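### Crossover between regions is built into the intervention, but the power calculation assumes a full 10-point difference by actual site while the primary comparison is by allocation

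*Combined protocol and SAP*

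**What the plan says.** **Insertion rule (section 5.6, Interventions).** A limit is set for the allocated side: "A maximum of two attempts will be allowed in the designated region". Once that limit is reached, the rule provides for a change of side: "following which further attempts will be considered in the non-designated region if the inserter is confident of success". Crossover is therefore planned conduct, not a deviation. The same section has the data captured: "Number of attempts at insertion and sites of attempts will be recorded as per unit protocol". The tracking sheet also holds the site of insertion.

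**Sample size (section 7.1).** The starting rate comes from the centre's retrospective study, where "the rate of PICC complication resulting in removal of PICC was 30" percent. The target is set as follows: "In order to find a clinically important difference of 10" percent, taken between lines inserted through the upper and the lower extremity. The result is 153 infants per group at 80% power and 5% alpha, with 320 to be recruited. No crossover rate or allowance is stated, and the 14 infants above 2 × 153 = 306 are not explained.

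**Analysis (section 7.2).** "Data will be analyzed using intention-to-treat analysis". The primary outcome "is a binary outcome where we will use chi-squared test or Fisher exact test". A secondary model is also planned: "multivariate logistic regression analysis to examine the association of PICC site and complication rate after adjusting for gestational age, day of PICC insertion and illness". The last of these covariates is a severity score. The section does not say whether PICC site there means allocated or actual site. It names no per-protocol or complier analysis.

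**Purpose (sections 2, 3, 4 and 11).** The question, hypothesis, objective and impact statement are all framed around the site of the line.

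**The concern.** Two different quantities are in play. Section 7.1 sizes the trial for a difference between sites of insertion. Section 7.2 tests a difference between allocated groups. They coincide only if every line goes where it was allocated, and section 5.6 provides for the case where it does not.

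If site affects complications and some infants cross, each arm becomes a mixture of the two sites and the tested difference is smaller than the one powered. The stated 80% is then not the power of the test that will be done. The plan also does not say that its primary result concerns the region tried first, so a small or null difference could be carried over to the site question without the qualification it needs.

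**Working it through.** **Inputs.** From section 7.1: 30% event rate, 10-point difference, 80% power, alpha 5%, 153 per group, 320 in total. From section 5.5: 1:1 allocation, so 160 per arm. Two-sided testing is assumed, because the hypothesis in section 3 is non-directional and section 7.1 does not state sidedness. The 10% is read as absolute. Its direction is not given, so both 30% vs 20% and 30% vs 40% are shown. The crossover rate c is not in the documents; 5% to 20% is an assumed range.

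**Step 1: the plan's own figure.** The pooled two-proportion formula is

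n per arm = [1.96·√(2p̄(1−p̄)) + 0.8416·√(p₁(1−p₁)+p₂(1−p₂))]² / (p₁−p₂)².

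For 30% vs 20%: (1.96·√0.375 + 0.8416·√0.37)² / 0.01 = (1.2002 + 0.5119)² / 0.01 ≈ 293.2, that is, 294 per arm. For 30% vs 40% it gives 356. The one-sided 30% vs 20% figure is 231. None gives 153. A single-group test against a fixed 30% does match: (1.96·√0.21 + 0.8416·√0.16)² / 0.01 ≈ 152.5, rounded up to 153. So the stated figure is too small before crossover enters.

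**Step 2: dilution.** Suppose the outcome follows the actual site, infants who cross have the same site-specific risks as the others, and a fraction c crosses in each arm. Then

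arm rate = (1−c)·own-site risk + c·other-site risk, and difference = 10·(1−2c) points.

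At c = 10%, the rates are 0.9·30 + 0.1·20 = 29% and 0.9·20 + 0.1·30 = 21%, a difference of 8 points.

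**Step 3: power of the allocation contrast at 160 per arm.**

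Power = Φ{[Δ·√160 − 1.96·√(2p̄(1−p̄))] / √(p₁(1−p₁)+p₂(1−p₂))}.

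At c = 0 this is Φ{(1.2649 − 1.2002)/0.6083} = Φ(0.106) = 54.2%. At c = 10% it is Φ{(1.0119 − 1.2002)/0.6098} = Φ(−0.309) = 37.9%.

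| c in each arm | Difference (points) | Power, 30% vs 20% | n per arm for 80%, 30% vs 20% | Power, 30% vs 40% | n per arm for 80%, 30% vs 40% |
|---|---|---|---|---|---|
| 0 | 10 | 54.2% | 294 | 46.6% | 356 |
| 5% | 9 | 46.0% | 363 | 39.2% | 440 |
| 10% | 8 | 37.9% | 459 | 32.2% | 557 |
| 15% | 7 | 30.3% | 600 | 25.8% | 728 |
| 20% | 6 | 23.5% | 817 | 20.1% | 991 |

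If only the 30% arm crosses (30% vs 20%), 10% crossover gives 9 points, 46.5% power and 358 per arm; 20% gives 8 points, 38.8% and 447.

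**Step 4: separating the two problems.** For 30% vs 20%, the drop from 80% to 54.2% (25.8 points) is the sample size error alone. Crossover then takes a further 8.2 points at c = 5%, 16.3 at 10%, 23.9 at 15% and 30.7 at 20%. The dilution does not depend on the first error. Even if 153 were right, 10% crossover would need 153/0.8² ≈ 240 per arm. The rise from 153 to 160 would offset only c = (1 − √(153/160))/2 ≈ 1.1%.

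**Step 5: what the regression on PICC site can do.** If site means allocated, the model is an adjusted version of the allocation contrast and is diluted in the same way. If site means actual, it is a non-randomised comparison: crossing follows failed attempts and the inserter's confidence, so difficult access may drive both crossing and complications. None of the three listed covariates measures difficult access.

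**Step 6: what a complier estimate would do.** It divides the allocation difference by (1 − c_U − c_L), where c_U and c_L are the crossover fractions in the upper and lower arms. With 5% and 20%, the allocation difference is 10 × 0.75 = 7.5 points, and 0.075/0.75 = 0.10 recovers the site effect under the Step 2 assumptions. The interval is stretched by the same factor, so the test is essentially unchanged.

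**The case against.** **Crossover may be rare.** Section 5.3 requires venous access in both upper and lower body, and crossing needs two failed attempts plus a confident inserter. This stands as a reason not to assume a high rate. It does not make the rate zero, and 5% in each arm still costs about 8 points of power.

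**Intention-to-treat suits the stated use.** The impact section speaks of guiding the inserter's choice of site, which is made before insertion, and comparing allocated regions informs that choice. This stands, and intention-to-treat should remain primary. What is missing is a statement that this is its target and a power figure that matches it.

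**Site is not ignored.** A reader might infer that the site effect is never estimated, or that only intention-to-treat is planned. The documents do not support either reading: section 7.2 plans a regression on PICC site, and actual site is recorded. The supportable point is that the term is undefined and that neither meaning gives an undiluted, unconfounded answer.

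**A complier estimate is no cure.** It does not recover lost power. An infant with difficult access in both regions might cross whichever way it was allocated, which breaks monotonicity, and an infant with no line placed has no actual site. Both objections stand, so the estimate should be supportive only, with its assumptions stated.

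**Conclusion.** The concern holds in this form: the trial is powered for a difference by actual site, its primary test compares allocated groups, and the crossover that separates the two is permitted but not allowed for. Under equal crossover of 5%, 10% or 20%, a 10-point site effect (30% vs 20%) appears as 9, 8 or 6 points, with power at 160 per arm of 46%, 38% or 24%; the corresponding powers for 30% vs 40% are 39%, 32% and 20%. These figures rest on assumed crossover rates, two-sided testing, and outcome following actual site with the same site-specific risks for infants who cross.

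A reader might infer that crossover explains why power falls short of 80%. It does not by itself: power is 54% with no crossover, and up to c = 15% the sample size error is the larger part of the shortfall. A reader might also infer that a null result will be reported as site making no difference. The plan does not say so, and it does commit to a relative risk with a confidence interval. That misreading is a risk to guard against, not something the plan does.

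**What to change.** **Section 7.1.** Correct the two-group calculation first, then restate the power of the allocation contrast over a stated range of crossover rates, giving the direction of the 10-point difference and the sidedness. Adding a crossover rate to 153 would not repair the figure.

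**Section 7.2.**
- Keep intention-to-treat as primary and state that it estimates the effect of the region allocated for first attempts.
- Define PICC site in the logistic regression. If it means actual site, label the result non-randomised.
- Report crossover and failure to place any line, by arm.
- Prespecify a supportive complier-average estimate with allocation as instrument and site of the placed line as treatment. State its assumptions: failed attempts do not themselves change later risk; no infants who would cross under either allocation, or else a homogeneous effect; and a rule for infants with no line placed. State also that its interval is wider and that it does not restore power.

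**Cost.** Some wording and one extra analysis. Attempts, their sites and the final site are already recorded, and the insertion rule is untouched. The main downside is a less favourable stated power, which the corrected sample size calculation will bring in any case.
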